
Risks and benefits
	
Risks:
 
 • Electrocardiogram: Minor local skin irritation momentarily. • Blood pressure: Minor temporary discomfort, numbness, and/or tingling at the fingertips during cuff inflation, which will subside after cuff release. Bruising at the area where the cuff is inflated, which will disappear within a few days. • Finger blood pressure: Minor numbness, tingling, and bluish coloration at the fingertip. The finger cuff will be turned off between the research procedures, and these symptoms will subside. • Blood vessel response, ischemic preconditioning, and ischemia–reperfusion: Minor temporary discomfort, numbness, and/or tingling at the fingertips and toes during cuff inflation, which subside after cuff release. Bruising at the area where the cuff is inflated, which will disappear within a few days. • Handgrip and knee extension exercise: Minor fatigue and exhaustion momentarily. • Bosentan: We will administer a single dose of 125 mg of Bosentan orally. These dose and route are effective to improve blood flow response to exercise³⁰. Furthermore, Bosentan is well tolerated up to 2400 mg³¹. Therefore, we do not expect any adverse events caused by participation in the study. Minor effects that may be expected are headache and swelling. Nevertheless, we will consider the following³²: Chronic use of Bosentan has been associated with alterations in liver function. Additionally, studies in animals indicate that Bosentan may cause harm to an unborn fetus. Furthermore, there is a possibility of failure in contraception when Bosentan and hormonal contraceptives are co-administered. Therefore, out of an abundance of caution, we will exclude from participation in the study individuals with a history of liver disease, women who are pregnant, trying to become pregnant or breastfeeding, and women using hormonal contraceptives. Also, male participants will be informed about a possible risk of a decrease in sperm count due to using Bosentan. • Blood and endothelial cell sampling: Intravenous collection of blood and endothelial cells may include minor risks for local infection, local bruising, or occasional light-headedness. These risks are minimized by being performed under sterile conditions only by research personnel with the required training and experience with this technique. Blood drawn will not exceed 150 milliliters on any experimental testing day. To run the assays all at one time and avoid variability, samples will be stored in a –80° C freezer until analysis. After analysis, samples will be discarded into a container labeled with a biohazard sign and stored in secondary waste containers. All stored samples will be coded to protect confidentiality. The code-key will be kept in the Principal Investigator's
----------------------------------	---

	
office in a locked cabinet. Only the Principal Investigator and study personnel will have access to the files via key. No other students or faculty will have access.
 
 ACE and SEE questionnaires: Given the sensitive nature of the topics assessed with these psychometric tests, participants will be informed that they may experience some distress or discomfort, may decline to answer any question, and may request to interrupt or end the assessment at any time. Our research personnel will observe the participants and may also interrupt or end the assessment if it seems necessary. In the event of an emergent psychiatric crisis, [name] and the research personnel will take appropriate steps including calling an emergency contact person indicated by the participant in the Medical History Form, and facilitating transportation to emergency health care. Furthermore, all participants will receive referral information and telephone numbers for local and national emotional support services, such as the Student Counseling and Wellness Center, the Center for Integrative Health, the Behavioral Health Specialty Clinic, Crisis and Suicide Prevention lines. 
Benefits:
 
 There will be no direct benefit from participating in this research study. We hope to learn information that may help others in the future.
Randomization and blinding	
We will use a Randomization Model tool in the REDCap system to randomly select between Bosentan and Placebo to be administered on Visit 2 for each individual, aiming at achieving a balanced distribution between Black and White individuals, and between men and women. Once the random drug selection is made for Visit 2, selection for Visit 3 will automatically be the alternative drug. Therefore, participants who complete Visits 2 and 3 will have received both Bosentan and Placebo. The participants and study personnel will be blind to the administration of Bosentan or Placebo on any visit. Pharmacists of the Investigational Drug Services at UMMC will retain the information about the drug selection per visit and will reveal it to the study personnel after completing data collection and analyses for that study participant or in case of emergency health care.

Outcome Measures	The primary measurements obtained by duplex Doppler ultrasound are: 1) brachial artery flow-mediated dilation (i.e., the increase in arterial diameter in response to the increased shear stress following forearm cuff release); 2) forearm reactive hyperemia (i.e., the increase in blood velocity following forearm cuff release); 3) blood flow responses to passive leg movement; 4) blood flow responses to low, moderate, and high-intensity rhythmic handgrip exercise; 5) blood flow responses to low, moderate, and high-intensity rhythmic knee extension exercise. Other measurements are beat-to-beat heart rate and beat-to-beat blood pressure, which can be used for further analyses of heart rate variability, blood pressure variability, and baroreflex sensitivity.
Study Endpoint	To determine whether there is an augmented contribution of ET-1 to the basal vascular tone in Black individuals compared with White individuals. We anticipate that the antagonism of ET-1 receptors will improve vasodilator responses in Black individuals but not in White individuals.
Data Safety Monitoring Plan	[name] Jr., Professor of the Department of Medicine, will serve as an independent Data Safety Monitor for this study. The study personnel will conduct semi-annual meetings with the Monitor to present the research progress and discussion of observed events upon drug administration. In case of a participant's emergency health care that could be associated with the study, the study personnel will notify the Monitor within 24 h.
Protected Health Information (PHI)	The information collected in this study includes name, telephone, home address, e-mail address, date of birth, age, race and ethnicity, medical history, and pictures. Each study participant will be given a study ID and the data will be associated with this ID. All data will be accessed via HIPAA compliant methods and stored using REDCap.
Statistical Methodology	Flow-mediated dilation and reactive hyperemia will be compared between groups (Black vs. White) and between drugs (Bosentan vs. Placebo) using a mixed model ANOVA (two-way). Responses to rhythmic handgrip exercise will be compared between groups (Black vs. White), between drugs (Bosentan vs. Placebo), and between intensities (low, moderate, high) using a mixed model ANOVA (three-way).

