Purpose	
To begin to elucidate the alterations in vascular function in Black individuals, we chose to target ET-1, a peptide produced by the vascular endothelium that mediates vasoconstriction by binding ET_A and ET_B receptors on smooth muscle^{14,15}. ET-1 seems to play a prominent role in the pathophysiology of hypertension specifically in Black patients^{16,17}. Also, it is suggested that ET-1 may be associated with impaired vascular control of blood pressure in young normotensive Black men¹⁸. Vascular responsiveness to ET-1 is also upregulated in adults exposed to insults during their fetal life (e.g., poor maternal nutrition, chronic stress, no prenatal care), psychological stressors during childhood (e.g., physical and emotional abuse, household dysfunction), and high ethnic discrimination¹⁹⁻²⁴—all of which are more prevalent among Black than White individuals, possibly contributing to racial disparities in vascular function²⁵⁻²⁸. We hypothesize that Black individuals have reduced vasodilator responses as a consequence of a greater vasoconstrictor tone mediated by ET-1. Therefore, we hypothesize that the antagonism of ET_A and ET_B receptors will reduce the vasoconstrictor tone and augment the vasodilator responses in Black but not in White individuals.

Specific Aim	
We will examine the role of ET-1 on brachial and popliteal artery flow-mediated dilation, reactive hyperemia, and blood flow responses to passive leg movement, rhythmic handgrip exercise, and rhythmic knee extension exercise between Black and White individuals. Using an acute oral administration of Bosentan, we will antagonize ET_A and ET_B receptors to reduce the vasoconstrictor tone mediated by ET-1 and, consequently, allow for greater flow-mediated dilation, reactive hyperemia, and blood flow responses to passive leg movement, handgrip, and knee extension. We anticipate that this effect of Bosentan will be more prominent in Black individuals than in White individuals. In a separate visit, the participants will receive a Placebo to serve as a control. We will also examine prenatal and at-birth medical records, and apply questionnaires of adverse childhood experiences and perceived discrimination to assess whether these early-life risk factors are associated with racial disparities in vasodilation between Black and White individuals.

Study Period	
3 years Anticipated start date: 09/01/2020 Anticipated end date: 09/01/2023

Data Generation Period	N/A

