----------------------------	---

- ET-1 expression: Plasma and endothelial lysates will be collected from the antecubital vein using a catheter and J-wires. ET-1 peptide will be measured using an ELISA kit. RNA from endothelial cells will be isolated and reverse transcribed. The resulting cDNA will be used to quantify ET-1 mRNA copy count by Droplet Digital polymerase chain reaction using TaqMan primer gene expression assays with human preproET-1 primers.
- Insults during fetal life: Prenatal and at-birth medical records of each participant will be obtained from the UMMC and local hospitals database in paper copies and digital formats (*e.g.*, EPIC, DataArk). We will assess maternal comorbidities, such as over- or undernutrition, pre-eclampsia, diabetes, obesity, smoking, and alcohol consumption. Gestational age at birth will be assessed and classified as preterm (less than 37 weeks), early-term (37 weeks to 38 weeks 6 days), full-term (39 weeks to 40 weeks 6 days), late-term (41 weeks to 41 weeks 6 days), or post-term (over 42 weeks)²⁹. Also, the birth weight will be assessed, and birth weight of fewer than 2500 grams will be a marker of impaired fetal growth²⁶.
- Adverse childhood experiences: The questionnaire ACE will measure the prevalence of 10 types of trauma over the first 18 years of life: emotional abuse, physical abuse, sexual abuse, emotional neglect, physical neglect, household substance abuse, domestic violence against mother (stepmother), household incarceration, household mental illness, and parental divorce²⁷.
- Perceived discrimination: The questionnaire SEE will measure the magnitude of perceived discrimination, ethnic identity, mainstream comfort, and social affiliation²⁸.

Summary of Research Procedures

- Bosentan or Placebo: A single oral dose of Bosentan (125 mg; Tracleer, Actelion Pharmaceuticals US, San Francisco, CA) or Placebo will be administered in separate visits in a randomized, double-blind, crossover design. Bosentan is an FDA-approved medicine used for the treatment of cardiovascular diseases such as pulmonary hypertension. Pharmacists of the Investigational Drug Services at UMMC will prepare Bosentan and Placebo in liquid suspensions.

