Inclusion Criteria	
 • Black (i.e. African American) or White (i.e. Caucasian American) individuals • 18 to 35 years of age • Born and raised in the United States • Biological parents of the same race (i.e. either Black or White)

Exclusion Criteria	
 • Known chronic or ongoing disease, or on prescribed pharmacological treatment • History of liver disease • Pregnant, trying to become pregnant, or breastfeeding women • Use of hormonal contraceptives • Smoking or vaping in the last 6 months • Body mass index > 35 kg/m²
Number of Participants (anticipated)	
50 participants (i.e. 25 on each racial group). Based on data from Schreuder et al.³⁰, taking the improvement of blood flow response to rhythmic handgrip with Bosentan as the primary outcome, the estimated sample size is 42 participants (i.e. 21 per group). We anticipate having to recruit about 20% more individuals to account for possible loss of data (e.g. participants who cannot complete all visits, problems during analyses, etc.), therefore needing to enroll 50 participants.

Screening and Consent Process	
Announcements will be made via UMMC e-mail listserv, UMMC intranet, Research Participant Recruitment app, flyers on campus, and word of mouth. Potential participants will contact the study personnel via e-mail or phone, and answer screening questions. If they meet the inclusion criteria, Visit 1 will be scheduled. Consenting will be conducted in Visit 1 at the research clinic by [name] or by a study person after supervision and adequate training with [name]. Following consenting, there will be assessments of medical history, and familiarization with the research measurements and procedures. After that, those who qualify for the study will be scheduled for Visit 2 and, subsequently, Visit 3.

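### The fetal-growth marker is a fixed 2500 g birth-weight cut-off that ignores gestational age and sex, so it mixes prematurity with growth restriction and would flag few participants

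*Combined protocol and SAP*

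**What the plan says.** The Specific Aim of the Research Protocol adds an early-life objective to the bosentan comparison. Birth records and two questionnaires, on adverse childhood experiences (ACE) and on ethnic experiences and perceived discrimination (SEE), are to be used "to assess whether these early-life risk factors are associated with racial disparities in vasodilation between Black and White individuals".

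Under Study Design, the item on insults during fetal life sets out the record-based exposures:

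- Growth: "birth weight of fewer than 2500 grams will be a marker of impaired fetal growth". No adjustment for gestational age or sex is given.
- Prematurity: "Gestational age at birth will be assessed and classified as preterm (less than 37 weeks", followed by four further classes up to post-term. It is not combined with birth weight.
- Maternal factors: "We will assess maternal comorbidities, such as over- or undernutrition, pre-eclampsia, diabetes, obesity, smoking, and alcohol consumption".
- Source: "Prenatal and at-birth medical records of each participant will be obtained from the UMMC and local hospitals database".

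The Inclusion Criteria ask for "Born and raised in the United States", not for local birth. The section on number of participants estimates 42 people and enrols 50, based on the handgrip blood flow response to bosentan. Statistical Methodology covers comparisons by group, drug and exercise intensity. It gives no model for any early-life factor and no rule for a record that cannot be found.

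**The concern.** Birth weight depends on both length of gestation and growth for that length. A fixed weight threshold cannot separate the two. A healthy-sized baby born early can fall under 2500 g and be labelled growth-impaired. A baby born at term who is small for gestation but above 2500 g is labelled normal. The protocol treats prematurity as an exposure in its own right, so the marker partly repeats that exposure and measures growth poorly.

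A low threshold also flags few people in a sample of 50. The objective concerns differences between races, and with a handful of flagged people across both races, exposure and race are hard to tell apart. A null result would say little, and a positive one could reflect prematurity.

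A second, smaller issue is coverage. The record sources named are local and eligibility is national, so some participants may have no birth data at all.

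**Working it through.** **Inputs from the documents.** The estimated sample is 42, with about 20% more for losses and 50 enrolled (Research Protocol, number of participants). The cut-off is 2500 g (Study Design). A two-sided alpha of 0.05 and power of 80% are stated in Statistical Design and Power for the parent proposal; they are borrowed here because the 42-person estimate states neither. I use 50, not the parent proposal's 60, because the early-life objective appears only in the Research Protocol.

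**Assumptions.** The share under 2500 g is 5-15%, and the share of records retrieved is 50-100%. Neither figure is in the documents.

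**The plan's own figure.** 42 × 1.20 = 50.4, which agrees with 50. The 42 cannot be reproduced, because no effect size or standard deviation is given. The plan states no expected number exposed and no power for the early-life objective.

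**Expected number flagged** = 50 × share under 2500 g × share of records found.

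- Lowest: 50 × 0.05 × 0.50 = 1.25
- Middle: 50 × 0.10 × 1.00 = 5.0
- Highest: 50 × 0.15 × 1.00 = 7.5

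This gives about 1 to 8 people across both races.

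**What a flagged-versus-not comparison could detect** (two-sample t-test, 80% power, all 50 records). The normal approximation is (1.96 + 0.84) × √(1/k + 1/(50 − k)) for k flagged. At k = 5 it gives 2.80 × √(0.200 + 0.022) = 1.32 SD; the t-based value is 1.35.

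| Flagged of 50 | Detectable difference (SD) | Power for 0.8 SD |
|---|---|---|
| 2 | 2.06 | 19% |
| 5 | 1.35 | 38% |
| 8 | 1.10 | 53% |

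With 25 records and 2 flagged, the detectable difference is 2.16 SD.

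**Information kept by the split.** Assume a linear relation and a roughly normal birth weight. Cutting at the lower tail with probability p keeps φ(z)² / [p(1 − p)] of the information, where z is the normal quantile at p.

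- p = 0.08: φ = 0.149; 0.0221 / 0.0736 = 0.30
- p = 0.14: φ = 0.223; 0.0496 / 0.1204 = 0.41

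Fifty people analysed by the split are then worth about 50 × 0.30 = 15 to 50 × 0.41 = 20.5 people analysed on the continuous value. This applies only if the split is the form analysed.

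**Effect of mixing in prematurity.** If 30-70% of those flagged were small only because they were born early (an illustrative assumption), the observed contrast would shrink to about 70-30% of its true size. The actual number misclassified cannot be computed from the documents.

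**What a continuous measure could detect.** The smallest correlation at 80% power is tanh[(1.96 + 0.84)/√(n − 3)]. This is 0.39 with 50 records, 0.42 with 42 and 0.54 with 25.

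**The case against.** The best defence is that the protocol calls the threshold a marker and does not say it is the analysed variable. Birth weight and gestational age are both to be abstracted, and nothing forbids a continuous or gestation-adjusted analysis. The objective is secondary and plays no part in the sample size. All of this stands. It makes the information loss conditional on the split being analysed. It does not rescue the marker, which is the only growth measure defined, and no later section replaces it.

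Stronger readings that a reader might infer go beyond the documents:

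- **That the whole early-life objective rests on a handful of misclassified people.** It also uses maternal comorbidities, gestational age and the ACE and SEE questionnaires. The questionnaires are given at Visit 1 and need no hospital record. The extent of misclassification is not shown.
- **That prematurity is counted twice in the analysis, or that the continuous weight is discarded.** No early-life model is given, so neither can be established.
- **That participants born elsewhere will have no birth data.** The text names local sources without excluding others, and written consent for access to records carries no stated geographic limit. The Medical History Form is listed but not reproduced, so it may already ask for these values.
- **That records will be missing differently by race.** This is possible, but nothing in the documents shows it.

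The fix also has limits. Even with 50 complete records, only correlations of about 0.39 or more would be reliably detected.

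**Conclusion.** The point holds for the fetal-growth component. As defined, the marker confuses early birth with poor growth and misses small term babies above 2500 g. The 1 to 8 flagged participants rest on assumed prevalence (5-15%) and record coverage (50-100%). The 30-41% of information kept rests on an assumed 8-14% below the cut, a linear relation, near-normal birth weight, and the split being the form analysed. The flaw in the definition does not depend on any of these figures.

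The mismatch between local record sources and U.S.-wide eligibility is real but secondary, since its effect on coverage cannot be judged from the text. The ACE and SEE components and the primary drug-by-race comparison are not affected. The change is worth making because the better measure uses data the study already plans to collect.

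**What to change.** - Replace the 2500 g marker with birth weight for gestational age and sex as a continuous z-score. Name the reference in advance, and choose one suited to the years in which participants now aged 18 to 35 were born.
- Enter gestational age in weeks as its own variable, and keep the five classes for description.
- State the model and outcome for the early-life analysis, and label it exploratory.
- Say how missing or out-of-area records are handled. If the Medical History Form does not already ask, add two items: birth weight and weeks of gestation as reported by the participant or mother, for those without a retrievable record. Flag the source of each value, and repeat the analysis in participants whose values come from records.

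The cost is small: changed variable definitions, the choice of a reference and perhaps two form items. No visit, procedure or sample size changes. Reported values are less exact than records, which the source flag and repeat analysis address. The changed form needs approval as an IRB amendment (UMMC Investigator Responsibilities, item 5).

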Figure 4. Protocol of the experimental visits. Visits will be identical except for the oral drug or supplement administration before any procedure.

STATISTICAL ANALYSES: Sample size estimation (statulator.com) is 11 individuals per group, based on the femoral artery blood flow response to knee extension exercise from our preliminary data (see below), using Student's *t*-test for independent samples, and considering a two-tailed alpha of 0.05, and power of 0.8 as parameters. This estimated sample size is adequate relative to our previous investigations^{10,11}. Due to potential influence of sex and race on vascular function⁶⁹, we will duplicate the estimated sample size to recruit an equal number of men and women. To account for incompleteness and exclusion of data during analyses, additional participants will be recruited, leading to an estimate of 30 individuals enrolled in each racial group. We will use a mixed-model ANOVA to compare vascular responses according to the effects of drug administration (Placebo vs. Drug), group (Black vs. White), and interaction. Subjects' characteristics will be compared using Student's *t*-test for independent samples and, in case of significant differences, such characteristics will be used as covariates in the ANOVA. Additionally, while men and women will be primarily grouped according to race, the large and balanced sample size will allow for sub-analyses comparing the effects of race on vascular responses separately in men and women.

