Healthy Black and White men and women will be recruited between the ages of 18 to 40 years. The focus of our research is to examine differences in vascular function associated with race. Therefore, to avoid individuals with impaired vascular function due to aging and comorbidities, we will recruit a relatively young cohort of participants.

INCLUSION OF WOMEN AND MINORITIES

This research proposal is designed to elucidate deleterious alterations in vascular function specifically in young Black individuals. Accordingly, Black men and women will be examined and, as traditionally done in previous studies in this field, results will be compared with those from White men and women. Subjects will qualify for the study if they identify their race and the race of their biological parents as being Non-Hispanic Black (i.e., African American) or Non-Hispanic White (i.e., Caucasian American). Individuals whose parents are mixed Black and White, or of other races (Hispanic or Latino, Asian, Native American, etc.) will not qualify for the study. To avoid confounding factors associated with lifestyle, only individuals born and raised in the U.S. will be included. We anticipate to include a total of 60 individuals, with a distribution of 15 Black men, 15 Black women, 15 White men, and 15 White women. While men and women will be primarily grouped according to race, this large and balanced planned sample size will allow for sub-analyses comparing the effects of race on vascular responses separately in men and women.

RECRUITMENT AND RETENTION PLAN

Individuals will be recruited via UMMC e-mail listserv, UMMC intranet, flyers on campus, and word of mouth. Potential participants will contact the study personnel via e-mail or phone, and answer screening questions. If they meet the inclusion criteria, a consenting and familiarization visit will be scheduled. Consenting will be conducted at the research laboratory by a study person. After signing the Informed Consent Form, participants will answer a medical history questionnaire, and be familiarized with the research measurements and procedures.

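### The ET-1 protocol sets 25 participants per racial group with no split by sex and no sex term in its models, although the research plan for the same Bosentan crossover calls for equal men and women in each race

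*Combined protocol and SAP*

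**What the plan says.** Two parts of the combined document describe the same Bosentan crossover.

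**Research plan (Aim 2).** Research Strategy, Statistical Analyses, and again Statistical Design and Power, cite a possible influence of sex on vascular function and then state: "we will duplicate the estimated sample size to recruit an equal number of men and women". Inclusion of Women and Minorities anticipates 60 people, with "a distribution of 15 Black men, 15 Black women, 15 White men, and 15 White women". The model has drug, group and their interaction. Characteristics that differ significantly between the groups on a t-test are to be added as covariates, and sub-analyses compare the races within each sex.

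**ET-1 Research Protocol.** Number of Participants gives "50 participants (i.e. 25 on each racial group"), built from 21 evaluable per group plus an allowance for data loss. Neither that row nor the eligibility criteria set a number, proportion or cap by sex. One exclusion that in practice falls on women is "Use of hormonal contraceptives"; pregnancy, trying to conceive and breastfeeding are others. Randomization and blinding describes the choice of drug for Visit 2 as "aiming at achieving a balanced distribution between Black and White individuals, and between men and women". Statistical Methodology lists a two-way ANOVA (group, drug) and a three-way ANOVA (group, drug, intensity). It has no sex factor, covariate rule or analysis by sex.

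**The concern.** Race is not randomised, so the race comparison is only as good as the balance of the two groups on other determinants of the outcome. The research plan itself names sex as one of these and protects against it by equal recruitment. The ET-1 protocol does not carry over that protection and puts no adjustment in its place.

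Three terms need to be kept apart:

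- **Race main effect.** Exposed whenever the share of men differs between the groups and sex affects the response.
- **Drug x race.** This carries the hypothesis that Bosentan helps Black but not White participants. It is exposed only if, in addition, the Bosentan effect differs by sex.
- **Bosentan vs placebo within person.** Not exposed, because each participant is their own control.

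The Visit 2 randomization cannot help. It can balance which drug comes first within race and sex, but not how many men and women enter each racial group.

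**Working it through.** **1. The plan's own figure.** The protocol states "the estimated sample size is 42 participants (i.e. 21 per group") and "We anticipate having to recruit about 20% more individuals to account for possible loss of data". 42 x 1.20 = 50.4, stated as 50, so the figure reproduces. Half of 50 is 25 per group. Both 25 and 21 are odd, so neither divides equally by sex. The research plan has 60, that is 4 cells x 15.

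**2. Bias formula.** For an unadjusted race contrast, bias = (difference in share of men) x (sex effect). In within-sex SD units:

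- 15 vs 10 men of 25: difference 5/25 = 0.20. A sex effect of 0.5 SD gives 0.10 SD; 1.0 SD gives 0.20 SD.
- 16 vs 9 men: difference 7/25 = 0.28. A sex effect of 0.5 SD gives 0.14 SD; 1.0 SD gives 0.28 SD.
- Same split in both groups: bias 0.

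The documents give no sex effect, so 0.3 to 1.5 SD is an assumed range.

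**3. False-positive rate for the race contrast.** Simulated two-sample t-test, 25 per group, no true race difference, two-sided 5%:

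| Men per group | 0.3 SD | 0.5 SD | 1.0 SD | 1.5 SD |
|---|---|---|---|---|
| 15 vs 10 | 5.1% | 5.6% | 7.0% | 7.9% |
| 16 vs 9 | 5.8% | 6.9% | 11.3% | 16.6% |

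**4. How likely such gaps are.** Difference between two Binomial(25, 0.5) counts, computed exactly:

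- gap of 5 or more men: 20.3%
- gap of 7 or more: 6.5%
- gap of 10 or more: 0.7%

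Averaged over this chance imbalance, the simulated error rate is 4.9 to 5.1% for sex effects of 0.5 to 1.5 SD. If one group recruited 60% men and the other 40% (an assumption), it would be 6.5%, 9.5% and 13.6% at 0.5, 1.0 and 1.5 SD.

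**5. Would the research plan's covariate rule catch it?** Applying its t-test to sex coded 0/1:

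- 15 vs 10: p = 0.16, so not triggered
- 16 vs 9: p = 0.049, so only just triggered (Fisher's exact test gives 0.089)

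The rule does not appear in the ET-1 protocol and does not name sex.

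**6. Is equal enrolment enough without a sex term?** With 12 men in each group of 24, or 13 in each group of 26, and a 1 SD sex effect, the unadjusted test rejects in about 2.8% of null trials instead of 5%. The bias is gone, but the sex variance stays in the error term and the test is conservative. Enrolment targets also cannot guarantee balance among completers after the anticipated data loss.

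**The case against.** The strongest reply is that the harm is small. Chance imbalance is not a systematic bias, since averaged over it the unadjusted test keeps its 5% level. Systematic bias needs recruitment that differs by sex between the races, and the documents give no figures for that. The sample size rests on the improvement in handgrip blood flow with Bosentan, a within-person change, whereas the higher error rates belong to the race main effect. If the research plan governs Aim 2 on sex balance, its covariate rule arguably governs too. All of this limits the size of the point. It does not remove it: the covariate rule is absent from the ET-1 protocol and misses a 15 vs 10 split, and a known imbalance in the one trial that is run still affects how that trial's race contrast is read.

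A reader might infer more than the documents support:

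- **That false-positive rates above 20% are to be expected.** An 18 vs 8 split with a 1 SD sex effect gives 22%, but a gap of 10 or more men has probability 0.7% under 50:50 recruitment.
- **That the exclusions falling on women make the sex mix differ by race.** They apply to both races, and nothing in the documents shows an unequal effect.
- **That recruitment closes at 25 whatever the mix.** The number is labelled as anticipated and no closing rule is given.
- **That a cell will be nearly empty.** At 50:50, a given sex has 5 or fewer of 25 with probability 0.2%.
- **That the 15-per-cell distribution is binding.** It is worded as anticipated; the equal-number intention itself is stated directly.

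**Conclusion.** The point holds as a gap between two parts of the document. A safeguard that the research plan adopts for a stated reason is missing from the ET-1 protocol's enrolment target, and nothing in that protocol's randomization or models replaces it.

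The expected size is modest. It is negligible on average if both groups recruit men and women alike, and it becomes material only if the trial ends with a marked gap or the groups recruit differently by sex. These sizes rest on an assumed sex effect and an unadjusted analysis. The drug x race test needs the further assumption that the Bosentan response differs by sex. The change is worth making because it is cheap and protects a non-randomised comparison.

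**What to change.** **Number of Participants (ET-1 protocol).** Reconcile with Statistical Analyses and Inclusion of Women and Minorities by stating the same number of men and the same number of women in both racial groups, and close each cell when full. Within the stated 50, 13 women and 12 men in each race would do: not exactly equal within a race, but identical across races, which is what removes the bias. If exact equality is wanted, the nearest group sizes are 24 (12 + 12) or 26 (13 + 13). The difference between 50 and 60 participants should be settled at the same time.

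**Statistical Methodology (ET-1 protocol).** Add sex as a prespecified factor, with sex x drug when drug x race is tested, regardless of any baseline significance test. This recovers the precision that a quota alone leaves in the error term and covers imbalance arising from data loss.

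**Cost.** With the 13 + 12 split, no extra participants. The scarcest cell may fill more slowly, and the model loses one or two degrees of freedom.
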